The participants will be randomized to treatment with sealed therapeutic shoe or TCC. The randomization will be stratified for ulcer size (smaller or bigger than 1 cm^2 , ulcer size calculated as longest diameter*longest perpendicular diameter) and study center, and use random permuted blocks of randomly varying size.

Recruitment of participants

People who fulfill the inclusion criteria and not the exclusion criteria will be given oral and written study information and asked about whether they are interested in participating in the study. Those who agree will sign an informed constant to participate.

Intervention group, sealed therapeutic shoe: A prosthetist/orthotist will try out new therapeutic shoes to the participants and make individual insoles after casts of the feet. There will a limited number of shoe types to choose between and the procedure and material for the insole production will be standardized. The ulcer will be offloaded by adjusting the insoles with the help of plantar pressure measurement using the F-scan system (Tekscan, Boston, MA, USA). The “seal” of the shoe consists of a soft plastic strip (Bracelok, DJO Nordic, Malmö) that have to be broken to remove the shoe.

[figure not shown]
Control group, TCC: The participants will be treated with TCC, applied in a standardized manner. Participants in this group will also receive shoes and insoles, according to the same protocol as above, before TCC treatment is initiated to be comparable to the other group in the long-term follow-up after healing, when both groups will use shoes and insoles to prevent reulceration.

Both groups will visit the cast technician 1-2 times/per week depending on the status of the ulcer. The cast technician will change dressings, note whether the seal has been broken (for the intervention group), change casts (for the control group), photograph and document ulcers and complications, and ask participants if they have experienced any issues with the treatment. After this, a new dressing is applied, and the shoe is sealed (intervention group) or

a new cast is applied (control group). Participants will use a cover on the shoe or cast while taking a shower, and for the intervention group a cover will also be used when sleeping. Both groups will receive written information about potential complications and contact information to the clinics.

Data collection

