2.7 TIMING OF OUTCOME ASSESSMENTS

Table 1 below lists outcomes and time points for assessments (base-line, 4 weeks into treatment, and 1, 6 and 12 months after treatment end). For the 4 week into treatment and 1 month post-treatment assessments, a visit window of ± 1 week will be used. For the 6 and 12 months post-treatment assessments, a visit window of ± 1 month will be used.

Table 1. Overview of variables and assessment methods.

Variable (scale level: nominal=N, ordinal=O, interval=I)	Assessment method	Assessment occasion				
		Treatment period		Follow-up after treatment end		
		Base- line	4 weeks	1 month	6 months	12 months
Ulcer healing (N)	Clinical observation + blinded photo	X	X	X		
Skin complications (N)	Clinical observation + blinded photo	X	X	X		
Glycemic control (I)	Blood sample (HbA1c) ^a	X	X	X	X	X
BMI (I)	Measurement of weight and height	X	X	X	X	X
Gait function (I)	10 meter walk test ^{b 17}	X	X	X	X	X
Gait function (I)	Timed up and go ^{b 18}	X	X	X	X	X
Balance (O)	Berg balance scale ^{b 19}	X	X	X	X	X
Muscle atrophy (I)	Calf circumference ^{a 20}	X	X	X	X	X
General quality of life (O)	RAND-36 ^{c 21} , EQ-5D-5L ^{c 22}	X	X	X	X	X
Disease-specific quality of life (O)	DFS-SF ^{c 23}	X	X	X	X	X
Physical activity (I)	ActivPAL ^{d 24}	X	X	X	X	X
Physical activity (O)	National Board of Health and Welfare's indicator questions ²⁵	X	X	X	X	X
Bone mass density (I)	DXA ^e (heel bone)	X		X	X	X
Locus of control (O)	Questions from MHLC-C ^{c 26}	X		X	X	X
Ankle range of motion (I)	Goniometer ^{a 27}	X		X	X	X
Ankle strength (I)	Dynamometer ^{a 28}	X		X	X	X
Adherence to therapeutic shoes (O)	Questions from Q-TFA ^{c 29}	X		X	X	X
Treatment satisfaction (O)	Visual analogue scale ^c		X	X		
New ulcers, amputations, death, Charcot foot (N)	Patient file and self-report ^c				X	X
Health care consumption (O) ^f	Patient administration systems and self-report ^c			X	X	X
Sick leave from work (I) ^f	Self-report, ^c Swedish Social Insurance Agency's system			X	X	X

^aStandardized method, ^bfunction test, ^cquestionnaire, ^dactivity monitor, ^eDual-energy X-ray absorptiometry ^ffor the of health-economic analysis.

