5.2.2 SECONDARY EFFICACY ENDPOINTS

Secondary outcome measures (variables and assessment methods) are listed in Table 1. The cast technician will document and take photographs of skin complications. A physiotherapist will perform the standardized assessments (calf circumference, etc.) and function tests (gait, balance, etc.).

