5.3 SAFETY ASSESSMENTS

5.3.1 ADVERSE EVENTS

Adverse events that are judged to be related to the offloading devices (shoe or TCC) will be classified as adverse device effects (ADE) and serious adverse device effects (SADE).³² ADE include, but are not limited to, skin abrasions, blisters, sleep disturbances, issues with gait and balance, etc. SADE include, but are not limited to, new foot ulcers that result in amputation (major amputation = above ankle, minor amputation = below ankle), sepsis, etc.

Averse events that are not related to the offloading devices are classified as adverse events (AE) and serious adverse events (SAE).³² AE include, but are not limited to, skin abrasions or new foot ulcers on the contralateral foot and not related to the device, etc. SAE include, but are not limited to, death, amputation, onset of acute Charcot foot, sepsis, etc. (not related to the offloading device). However, in accordance with previous studies on similar patient populations, not all AE and SAE will be included as the patient population suffers from multiple co-morbidities and therefore a high incidence of illness and hospital admissions unrelated to the DFU and offloading devices can be expected.³³ Therefore, all ADE and SADE will be assessed, but only certain types of AE and SAE that are of particular interest, such as, amputation, death and onset of acute Charcot foot.

ADE, SADE, AE and SAE will be assessed with the aid of questionnaires, CRF, photographs of ulcer and skin, and patient files.

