6.1.2 ANALYSIS OF THE SECONDARY ENDPOINT(S)

The secondary analyses are not dependent on the findings of the primary endpoint. No adjustment for Type 1 errors will be used as only one or a few statistical tests will be conducted for each secondary endpoint.

The secondary endpoints are time to healing and measures listed in Table 1. Each secondary endpoint is measured between one and five occasions during the study. The ITT dataset will be used for all analyses of secondary endpoints. Adjusted analyses will only be conducted for certain secondary endpoints that are of particular interest.

Time to healing will be compared between the study groups using survival analysis. Kaplan-Meier survival curves will be produced for the two study groups with median healing times and 95 % CI. Participants for whom the ulcer has not healed will be treated as censored and their date of trial exit or date of last available assessment will be used to calculate their duration in the trial. Hazard ratio with

95% CIs will be presented. Treatment effect will be explored using a Cox proportional hazards model including stratification factors (ulcer area and depth at baseline, periphery artery disease and infection grade) initially.

Survival analysis as above (but without adjustment) will also be used to compare ulcer recurrence after healing between the study groups. Recurrence rates at 12 months after healing will also be compared.

The analysis of the other secondary endpoints will be conducted according to scale level (nominal, ordinal or interval; Table 1) and compared at each time point (base-line, 4 weeks into treatment and 1, 6 and 12 months post-treatment) using the ITT dataset without adjustment for covariates: t-tests for ordinal and interval data if the assumptions of the t-test is fulfilled (normal distribution and equal variances), otherwise Wilcoxon rank sum test will be used. The Chi-squared test or generalized linear regression method will be used for nominal scale data. For each comparison both exact p-values and two-sided 95% CI will be reported.

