6.1.3 SAFETY ANALYSES

Safety endpoints during the treatment period will be reported as summary statics (number and percentage) per study group. They will be categorized as AE, SAE, ADE and SADE (see point 5.3 above) and the proportions will be compared between the study groups with statistical tests for nominal scale data, that is, Chi-square test and presenting exact p-values and two-sided 95% CI.

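### Skin complications are planned to be compared visit by visit, with week 4 the only visit on the device; no planned test compares them as such over the treatment period

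*SAP*

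**What the plan says.** **Schedule.** Table 1, in both the Protocol and SAP 2.7, marks skin complications at baseline, 4 weeks and 1 month after treatment end. SAP 2.7 adds: "For the 4 week into treatment and 1 month post-treatment assessments, a visit window of ± 1 week will be used". The table gives no look-back period for the row.

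**Test.** Under SAP 6.1.2, secondary endpoints other than time to healing and recurrence are "compared at each time point (base-line, 4 weeks into treatment and 1, 6 and 12 months post-treatment". Nominal data get a chi-squared test or a generalized linear regression.

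**Data.** Both arms see the cast technician 1-2 times a week. The Protocol (Methods, description of the two groups) has the technician "photograph and document ulcers and complications" at these visits. SAP 5.2.2 confirms the source: "The cast technician will document and take photographs of skin complications".

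**Safety.** SAP 5.3.1 states: "ADE include, but are not limited to, skin abrasions, blisters, sleep disturbances, issues with gait and balance, etc". SAP 6.1.3 states: "Safety endpoints during the treatment period will be reported as summary statics (number and percentage) per study group". The groups are then compared on proportions by AE, SAE, ADE and SADE. Of the events not related to the device, only selected types are assessed.

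**Objective.** Objective 2 (SAP 1.2) asks about a difference in adverse events during the treatment period, tested two-sided.

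**The concern.** At baseline no device has been worn. One month after treatment end, both arms are due to be in the same kind of shoes and insoles. Of the three scheduled comparisons of skin complications, only week 4 can therefore show a difference between devices while they are worn. That is one look within a treatment period whose length varies by participant, for an objective that covers the whole of it.

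The count over the whole period exists, but only by category. A blister or abrasion enters it if judged device-related, and then sits with sleep, gait and balance complaints. A skin lesion judged unrelated may not enter at all.

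Skin damage is a main way in which these devices could differ: the Protocol's background notes that a TCC can cause secondary ulcers. As planned, the report could show no skin difference at week 4 beside a difference in the pooled ADE proportion, with no rule for which result answers the skin question.

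**Working it through.** The documents give no rate, duration or power for skin complications, so there is no figure of the plan's to reproduce. The check asks how much a week-4 comparison could see.

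**Inputs from the plan**
- 90% healed at 12 weeks in both arms (SAP 2.3).
- 56 per arm (recruitment floor) or 75 per arm (150 / 2).
- Two-sided 5% test (SAP 3.1).

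**Assumptions**
- Constant healing hazard, with device time capped at 12 weeks.
- New lesions start at a constant weekly rate λ on the device: 0.05, 0.10 or 0.15 for TCC, and one third of that for the shoe.
- A lesion lasts L = 1, 2 or 3 weeks.

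**Step 1: time on device**
- Hazard h = ln(10) / 12 = 0.1919 per week.
- Still on device at week 4: exp(-4h) = 46%.
- Mean device time to week 12: (1 - 0.1) / h = 4.69 weeks. Mean device time in weeks 0-4: (1 - 0.464) / h = 2.79 weeks.
- Share of device time after week 4: 1 - 2.79 / 4.69 = 40%.

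**Step 2: proportion of participants counted under each rule**
- Any time in treatment: λ/(λ+h) × [1 - exp(-12(λ+h))].
- Week-4 entry covering weeks 0-4: the same with 4 in place of 12.
- Week-4 entry meaning present that day: exp(-h(4-L)) × λ/(λ+h) × [1 - exp(-L(λ+h))].

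TCC in the middle case (λ = 0.10, L = 2), where λ/(λ+h) = 0.3426:
- Any time: 0.3426 × 0.970 = 33.2%.
- Weeks 0-4: 0.3426 × 0.689 = 23.6%.
- Present that day: 0.681 × 0.3426 × 0.442 = 10.3%.

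The shoe at one third of that rate gives 13.8%, 8.8% and 3.7%.

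**Step 3: share of ever-affected TCC participants that week 4 captures**

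| Meaning of the week-4 entry | Middle case | Range over λ and L |
|---|---|---|
| Present that day | 10.3 / 33.2 = 31% | 13-54% |
| Any event in weeks 0-4 | 23.6 / 33.2 = 71% | 66-76% |

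**Step 4: power of the two-sided 5% chi-square, middle case**

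| Per arm | Present that day | Weeks 0-4 | Any time in treatment |
|---|---|---|---|
| 56 | 27% | 58% | 70% |
| 75 | 37% | 71% | 81% |

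If the shoe rate is half the TCC rate, the figures at 56 per arm are about 15%, 32% and 37-38%.

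**Step 5: cross-check without the healing model.** For a fixed treatment length T and exponential lesion duration with mean D weeks, the share of events still present at week 4 is D(1 - exp(-4/D)) / T.
- D = 1, T = 12: 0.982 / 12 = 8%.
- D = 3, T = 6: 3 × 0.736 / 6 = 37%.
- The share passes half only for long lesions and short treatment (D = 4, T = 5: 51%).
- If the entry covers weeks 0-4, the share is 4 / T: 67% at T = 6 and 33% at T = 12.

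**The case against.** **The week-4 entry need not mean present that day.** This stands. Table 1 has a mark and no look-back period. Other rows must look back: deaths, amputations and new ulcers are marked at 6 and 12 months. Ulcer healing has the same three marks as skin complications, yet it is assessed 1-2 times a week and analysed at 12 weeks. Table 1 is thus a loose schedule for what the technician records. A reader might infer that the planned test counts only lesions visible at week 4 and so misses most events. The documents do not support this. It depends on the presence reading and on assumed rates and durations, and under a weeks 0-4 reading most affected participants are captured in the healing model.

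**The safety analysis covers the whole period.** This also stands. A device-related blister in week 2 or week 6 counts in the ADE comparison of 6.1.3, so a reader would be wrong to infer that such events are lost to the plan. Nor need the two results contradict each other, since they measure different things. Nothing in 6.1.3 forbids a breakdown by type, but none is planned, and a pooled ADE proportion does not answer a question about skin.

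**A whole-treatment test may also be weak.** True: with a halved rate it has under 40% power at 56 per arm. It is still the strongest of the three counts in every case computed here.

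**Conclusion.** The point holds as a gap between Objective 2 and the comparison named for skin complications. That comparison has one on-device time point with an undefined look-back, while records from visits 1-2 times a week go unused in any skin-specific test.

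Week 4 can miss many events; how many is not known. Under either reading of the entry, events after week 4 fall outside it, and these arise in about 40% of device time if healing follows a constant hazard to 90% at week 12. Treatment runs until healing, so slow healers may be on a device beyond the 12-week cap used here, which would raise that share. The capture and power figures rest on assumed onset rates, lesion durations and rate ratios, and they illustrate a range.

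This concerns one secondary outcome and leaves the primary analysis untouched. It is a cheap improvement.

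**What to change.** In SAP 6.1.2 and Table 1:
- Make the skin-complication comparison the proportion of participants with at least one new skin complication documented by the technician from device application to treatment end.
- Add a supporting rate per week on device, because treatment length varies between participants and could differ between arms.
- Keep the baseline, week-4 and 1-month comparisons as descriptive, and state the period that each entry covers.
- Draw the skin events in the ADE table from the same records, and show device-related skin events separately.
- Limit the endpoint to complications that technicians already document. The plan deliberately restricts adverse events unrelated to the device, and neither document says that the other foot is inspected at every visit, so the endpoint should not be widened to all causes on both feet.

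The cost is SAP wording and a little extra analysis, with no new visit or measurement. The small downside is more weight on records by technicians who can see which device is worn, partly offset by the blinded photo assessment that Table 1 already names for this row.

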2.3 SAMPLE SIZE

The sample size calculation was performed using <http://powerandsamplesize.com/Calculators/Compare-2-Proportions/2-Sample-Non-Inferiority-or-Superiority>. Primary outcome is proportion of healed ulcers after 12 weeks of treatment. Based on the literature and our feasibility study the proportion of healed ulcers after 12 weeks treatment is estimated to 90% with sealed shoe or TCC.^{15, 16} If accepting $p=0.05$, a statistical power of 80% and a non-inferiority limit of 10%, 112 participants are

needed. To compensate for attrition of participants during the long-term follow up of secondary outcomes, the aim is to recruit 150 participants. The participants will be randomized to treatment with sealed therapeutic shoe or TCC. However, if it turns out that it is too difficult to recruit 150 participants, the recruitment of participant will end when the primary end point (healing at 12 weeks) has been observed for 56 participants per group, giving a total of 112 which fulfils the sample size calculation.

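### SAP 6.1.2 leaves the baseline value unused in the follow-up comparisons of 15 secondary outcome rows; adjusting for it would add precision at little cost

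*SAP*

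**What the plan says.** SAP 2.7 sets the schedule: "Table 1 below lists outcomes and time points for assessments (base-line, 4 weeks into treatment, and 1, 6 and 12 months after treatment end". Its Table 1 gives the scale level of each row and shows which rows have a baseline value.

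SAP 6.1.2 says that the remaining secondary endpoints are "compared at each time point (base-line, 4 weeks into treatment and 1, 6 and 12 months post-treatment", and that this is done "using the ITT dataset without adjustment for covariates: t-tests for ordinal and interval data if the assumptions of the t-test is fulfilled". Failing those assumptions, "otherwise Wilcoxon rank sum test will be used". It adds that "For each comparison both exact p-values and two-sided 95% CI will be reported" and that "The ITT dataset will be used for all analyses of secondary endpoints".

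An earlier sentence in the same section leaves some room: "Adjusted analyses will only be conducted for certain secondary endpoints that are of particular interest". It names no endpoint. The only adjusted secondary analysis described is the Cox model for time to healing. No change score, ANCOVA or repeated-measures model is specified for the Table 1 rows.

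SAP 2.4 tests all secondary outcomes for superiority. No effect size, SD or power is stated for any of these rows. The numbers available to them come from SAP 2.3: "To compensate for attrition of participants during the long-term follow up of secondary outcomes, the aim is to recruit 150 participants", with a fallback that closes recruitment once the primary endpoint has been observed in 56 per group.

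**The concern.** The trial measures gait, balance, calf circumference, ankle function, quality of life and other outcomes before treatment, then sets those measurements aside when the groups are compared at follow-up. Baseline enters only as one more between-group comparison, where any true difference can only be due to chance because the groups were randomised.

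These rows contribute to Aims 2 and 3, alongside the adverse-event proportions of SAP 6.1.3 and the recurrence analysis of 6.1.2. The sample was sized for the primary endpoint, so precision on these rows is whatever that sample happens to give. A baseline value that predicts follow-up would narrow the confidence intervals without another visit or participant. It would also remove the part of a chance baseline difference that carries over to follow-up.

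**Working it through.** **The plan's own figure.** There is none for these rows. The one calculated figure in the documents, 112, belongs to the primary endpoint and does not enter this check; 56 per arm is used below only as a possible analysed number.

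**Counting the rows (SAP Table 1).** Ordinal or interval rows with a baseline value:

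- Four follow-ups (4 weeks; 1, 6, 12 months): HbA1c, BMI, 10 meter walk, timed up and go, Berg balance, calf circumference, RAND-36/EQ-5D-5L, DFS-SF, ActivPAL, activity questions. 10 × 4 = 40.
- Three follow-ups (1, 6, 12 months): bone density, locus of control, ankle range of motion, ankle strength, shoe adherence. 5 × 3 = 15.

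Total: 15 rows and 40 + 15 = 55 comparisons. Without ActivPAL, which SAP 6.1.7 treats as mainly exploratory, it is 55 − 4 = 51. With RAND-36 and EQ-5D-5L counted separately it is 55 + 4 = 59. Treatment satisfaction, health care consumption and sick leave have no baseline value and are left out.

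**How many suit ANCOVA.** Interval rows give 6 × 4 + 3 × 3 = 33. Berg, RAND-36/EQ-5D-5L and DFS-SF, if analysed as summary scores, add 3 × 4 = 12. The other 4 + 3 + 3 = 10 (activity questions, locus of control, shoe adherence) depend on scoring that the SAP does not state.

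**Size of the gain.** All inputs are assumptions: baseline-to-follow-up correlation r of 0.3 to 0.8, effect 0.4 SD, roughly normal outcome, two-sided 5%. 75 per arm is the 150 target without attrition, 56 the fallback, and 40 an illustrative late visit.

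SE of the difference in SD units = √(2/n) × √(1 − r²), with r = 0 for the unadjusted test. Power = Φ(0.4/SE − 1.96). Example at n = 56: √(2/56) = 0.189. Unadjusted: 0.4/0.189 − 1.96 = 0.157, power 0.562. With r = 0.5: SE = 0.189 × 0.866 = 0.164, 0.4/0.164 − 1.96 = 0.48, power about 0.69.

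| | unadjusted | r = 0.3 | r = 0.5 | r = 0.7 | r = 0.8 |
|---|---|---|---|---|---|
| Variance factor | 1 | 0.91 | 0.75 | 0.51 | 0.36 |
| CI width factor | 1 | 0.95 | 0.87 | 0.71 | 0.60 |
| Power, 40 per arm | 43% | 47% | 54% | 71% | 85% |
| Power, 56 per arm | 56% | 60% | 69% | 84% | 94% |
| Power, 75 per arm | 69% | 73% | 81% | 93% | 98% |

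At r = 0.5, 56 per arm is worth 56/0.75 ≈ 75 per arm unadjusted.

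**Chance imbalance.** The probability of a baseline difference beyond 0.2 SD in either direction is 2 × [1 − Φ(0.2/√(2/n))]: 37%, 29% and 22% per outcome at 40, 56 and 75 per arm. Such a difference shifts the expected unadjusted follow-up difference by at least r × 0.2, that is 0.06 to 0.16 SD.

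**Cost of the strata.** The table adjusts for baseline only. The number of sites is not given, so 2, 5 and 10 were assumed and simulated (5,000 runs per case, strata that explain nothing). The largest loss from adding site and ulcer area was 1.8 points (40 per arm, 10 sites, r = 0.5: 0.522 to 0.504). At r = 0.3 in that setting, power was 0.439 with baseline and strata, 0.450 with baseline alone and 0.415 unadjusted.

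**Skewed outcomes.** Simulated log-normal data, 56 per arm, 20,000 runs per case. The Wilcoxon test has power 53–54%. ANCOVA on the log scale has 59%, 68%, 84% and 93% at the four r values. ANCOVA on the raw scale with strong skew (log-SD 1) has 41%, 45%, 57% and 68%, below Wilcoxon for r of 0.5 or less. The scale therefore has to be chosen with care.

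**Missing baseline values.** Simulated at 56 per arm with 10% missing at random over participants (4,000 runs):

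| r | unadjusted | complete-case ANCOVA | pooled mean + indicator |
|---|---|---|---|
| 0.3 | 0.554 | 0.540 | 0.581 |
| 0.5 | 0.559 | 0.633 | 0.664 |
| 0.8 | 0.547 | 0.906 | 0.890 |

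**The case against.** The strongest reply is that nothing here is wrong. Unadjusted t-tests and Wilcoxon tests are valid in a randomised trial, every row is secondary, and the plan claims no power for them. The gain rests on correlations that the documents do not give and on one assumed effect; at r = 0.3 it is about 4 points before the strata are paid for. All of this stands, and it makes the point an improvement rather than an error.

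A second reply is that the plan already allows adjusted analyses for selected secondary endpoints. It does, but it names neither endpoints nor covariates, and the sentence governing these rows rules adjustment out. The allowance would leave the choice open until after the data are seen.

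A third reply concerns the remedy where the Wilcoxon test would apply. Taking the p-value from a rank ANCOVA and the interval from an unadjusted Hodges-Lehmann estimate would be worse than the present plan on one count. In two sets of simulations at 56 per arm with a 0.4 SD effect, the two disagreed on significance in 9–10%, 17–19%, 30–31% and 38–39% of trials at r = 0.3, 0.5, 0.7 and 0.8. That objection is right, and the fix below avoids the pairing.

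A reader might infer that leaving out the covariate biases these comparisons. The documents do not support that: randomisation protects the unadjusted test, and chance imbalance is a matter of precision. A reader might also infer that adjustment would make the post-treatment comparisons secure. It would not. The protocol's data collection section times the 1, 6 and 12 month visits from healing, so 15 × 3 = 45 of the 55 comparisons are at visits whose timing depends on an outcome of treatment. That is a separate issue, which baseline adjustment leaves untouched.

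**Conclusion.** The point holds as a cheap improvement confined to secondary outcomes. SAP 6.1.2 does not use the outcome's own baseline in any of the 55 row-by-visit follow-up comparisons, and those values are already collected. The figure 55 counts table rows; it is not a ceiling on tests, since subscales would add more.

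For roughly normal outcomes, confidence intervals would be 5% to 40% narrower over r = 0.3 to 0.8. With 56 per arm and a 0.4 SD effect, power would rise by about 4 to 38 points, less up to about 2 points for the strata. The size depends wholly on r, which the documents do not give and which will differ between rows. The gain does not extend to outcomes that stay on the Wilcoxon test.

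**What to change.** In SAP 6.1.2, for interval outcomes and summary scores with a baseline value:

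1. Make the main analysis at each post-baseline visit an ANCOVA adjusted for the outcome's own baseline and the randomisation strata of SAP 2.2 (site, ulcer area). Report the adjusted difference, its two-sided 95% CI and its p-value from that one model. Name the strata explicitly, because the Cox sentence in 6.1.2 lists a different set as stratification factors.
2. For outcomes named in advance as skewed, fit the model on the log scale and report a ratio of geometric means.
3. Use a single rule: fix the scale for each row before groups are compared, in place of the present rule that depends on checking t-test assumptions.
4. Where neither scale is suitable, and for single-item ordinal outcomes, keep the planned Wilcoxon test with its matching CI. Rank ANCOVA may be a sensitivity analysis, but its p-value should not be paired with an unadjusted CI. State the scoring of the activity questions, locus of control and shoe adherence.
5. Keep participants with a missing baseline value, for example by imputing the mean pooled over arms with a missing indicator. The reason is to preserve the ITT set; as the working shows, this does not always have more power than dropping them.
6. Remove baseline from the tested time points; SAP 5.1 and 6.1.4 already describe it.

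The cost is a change of wording, a little more analysis work and a few degrees of freedom for the strata. No new data, visits or participants are needed, and standard software is enough.

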1.2 HYPOTHESES AND OBJECTIVES

The overarching objective is to evaluate whether sealed shoe can heal DFU at least as effectively as TCC, but with fewer adverse events during the treatment period, better long-term effects and to a lower cost.

Specific objectives

Objective 1. To investigate whether a sealed shoe can heal DFUs at least as effectively as TCC (non-inferiority, one-sided hypothesis testing).

Objective 2. To investigate whether there is a difference in adverse events during the treatment period with sealed shoe and TCC (superiority, two-sided hypothesis testing).

Objective 3. To investigate whether there is a difference in long-term effects (up to 12 months after end of treatment) with sealed shoe and TCC (superiority, two-sided hypothesis testing).

Objective 4. To investigate whether there is a difference in health economic outcomes between treatment with sealed shoe and TCC (superiority, two-sided hypothesis testing).

The null hypotheses are that a sealed therapeutic shoe does not heal DFUs at effectively as TCC, and that there are no differences between sealed shoe and TCC in side-effects, long-term effects and health economic outcomes.

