2.4 FRAMEWORK

The primary outcome will be tested according to the non-inferiority hypothesis testing framework. All secondary outcomes will be tested according to the superiority hypothesis testing framework.

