3 STATISTICAL PRINCIPLES

3.1 CONFIDENCE INTERVALS AND P VALUES

In all analyses a 95% confidence level will be used as a cut off to declare statistical significance, and report both exact p-values and 95% CI. One-sided tests and CI will be used for the primary outcome and two-sided tests and CI the secondary outcomes. No adjustment for multiple comparisons will be used.

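### SAP 6.1.2 uses the Wilcoxon rank sum test as the remedy for unequal variances, which it is not; Welch's t-test, fixed in advance for each outcome, would be, and the quantity being estimated should be named

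*SAP*

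**What the plan says.** SAP 6.1.2 compares the secondary endpoints other than time to healing and recurrence at each time point, without covariates. For ordinal and interval data it plans t-tests "if the assumptions of the t-test is fulfilled (normal distribution and equal variances), otherwise Wilcoxon rank sum test will be used". The two conditions are joint, so failing either one leads to the rank-sum test. No check or threshold is named for either condition, and Welch's test is not mentioned.

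The same section adds: "For each comparison both exact p-values and two-sided 95% CI will be reported". It does not say what quantity the interval describes. SAP 3.1 sets the level ("In all analyses a 95% confidence level will be used as a cut off to declare statistical significance") and makes secondary tests two-sided, without adjustment for multiple comparisons. SAP 2.4 puts all secondary outcomes in a superiority framework. The null in SAP 1.2 is that "there are no differences between sealed shoe and TCC in side-effects, long-term effects and health economic outcomes", with no parameter named.

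**The concern.** The rank-sum test is a test of location only when the two distributions have the same shape and spread. The rule therefore moves an outcome to this test at the moment its key requirement has been judged to fail.

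One arm is immobilised at the ankle and the other is not, so spread as well as level could differ. The plainest candidates are gait, balance and calf circumference at the 4-week visit, while the cast is on.

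Two further consequences follow. The check is made at each visit, so the test, and with it the quantity compared, can change between visits for one outcome. And after a rank-sum test the reader is promised a 95% CI without being told what it is a CI for.

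**Working it through.** **Inputs from the documents.** Two-sided 5% level (SAP 3.1). 1:1 allocation (SAP 2.1). Arm sizes of 56 (the minimum in SAP 2.3) and 150/2 = 75 (the target). The plan gives no figure for this rule, so there is none to reproduce.

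**Assumptions.** SD ratios of 1 to 3, the distribution shapes, and the pre-tests (D'Agostino-Pearson in each arm and Levene, each at 5%). Arms of 75 and 56 stand for uneven loss. None of these is in the documents.

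**Step 1: normal data, equal means, by formula.** The rank-sum test uses the null variance V0 = (n1 + n2 + 1)/12, per n1·n2. If arm 2 has r times the SD of arm 1, the true variance per n1·n2 is

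V = 1/4 + (n1 − 1)·a + (n2 − 1)·b, with a = arcsin(r²/(1 + r²))/2π and b = arcsin(1/(1 + r²))/2π.

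The rejection rate is then about 2·[1 − Φ(1.96/√(V/V0))].

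- 56/56, r = 2: a = 0.1476, b = 0.0320. V = 0.25 + 55 × (0.1476 + 0.0320) = 10.13 and V0 = 113/12 = 9.417. V/V0 = 1.076, its root is 1.037, and 1.96/1.037 = 1.890, which gives 5.9%.
- 56/56, r = 1.5 and r = 3: V/V0 = 1.028 and 1.161, which give 5.3% and 6.9%.
- 75/56, r = 2, larger SD in the smaller arm: V = 0.25 + 74 × 0.1476 + 55 × 0.0320 = 12.93 and V0 = 132/12 = 11. V/V0 = 1.176, which gives 7.1%.
- Same sizes, larger SD in the larger arm: V/V0 = 0.976, which gives 4.7%.

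**Step 2: the whole rule, by simulation** (equal true means, 20,000 runs per setting; rejection rates).

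| Shape | n per arm | SD ratio | Plan's rule | Welch |
|---|---|---|---|---|
| Normal | 56/56 | 1.5 | 5.0% | 4.7% |
| Normal | 56/56 | 2 | 6.0% | 5.1% |
| Normal | 56/56 | 3 | 7.0% | 4.9% |
| Normal | 75/56 | 2 | 7.1% | 5.2% |
| Skewness 1 | 56/56 | 1.5 | 8.6% | 4.9% |
| Skewness 1 | 56/56 | 2 | 13.6% | 5.1% |
| Skewness 1 | 75/75 | 2 | 16.0% | 4.8% |
| Skewness 2 | 56/56 | 1.5 | 25.6% | 5.1% |
| Skewness 2 | 75/75 | 1.5 | 32.2% | 5.0% |

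The normal rows agree with step 1. Smaller separate runs gave 6.4% for the third row and 7.5% for the fourth. Runs with Shapiro-Wilk as the normality check gave up to 16.7% at skewness 1 with SD ratio 2, and up to 33% at skewness 2 with SD ratio 1.5. With equal spread the rule stays at 4.8% to 5.3% for every shape at 56 per arm, so skew alone does no harm.

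**Step 3: power.** With normal data, unequal spread and 56 per arm, Welch has about 2 points more power than the rule.

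**Step 4: switching between visits.** With normal data and equal SDs, the assumed pre-tests still send 15% of data sets to the rank-sum test. If five visits were independent, the test would change at least once with probability 1 − 0.85⁵ − 0.15⁵ ≈ 56%. Correlation between visits lowers this.

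**The case against.** Four objections carry weight.

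- **No mean is named.** A reader might infer that the plan declares mean differences that are not there. The documents do not support that: SAP 6.1.2 names no mean difference, and the null in SAP 1.2 is simply no differences. In the skewed settings with unequal spread the two distributions truly differ (the probability that one arm's value is below the other's is about 0.34 to 0.47, not 0.5). Rejection there is an error only if it is read as a difference in means. This objection stands. It bears less on the normal rows: means and medians are equal and that probability is 0.5, so the excess is wrong for any reading of location.
- **No CI for a mean is promised.** Also correct. A Hodges-Lehmann interval would satisfy the SAP's words. The gap is that the quantity is unnamed.
- **The variance condition is not the main cause of the large figures.** At equal SDs and 56 per arm, 85% to 100% of skewed data sets already reach the rank-sum test through the normality condition. In equal arms even the pooled t-test matches Welch (5.7% against 5.6% at skewness 2, SD ratio 2). So deleting the variance condition alone would not change the skewed case.
- **Welch is not free or perfect.** For a pure shift of 0.5 SD at 56 per arm, Welch has about 75% power, against 81% for the rank-sum test at skewness 1 and 95% at skewness 2. The reverse can occur: at skewness 1 with a 1.3-fold ratio, 78% against 74%. Under heavy lognormal skew (sigma 1) with SD ratios of 2 to 3, Welch itself rejects 6% to 8%.

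The affected list is also shorter than Table 1 suggests. Activity-monitor data are mainly exploratory (SAP 6.1.7), sick leave is collected for the health-economic analysis, and ankle strength is not measured at 4 weeks.

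**Conclusion.** The point holds in a narrow form. The rank-sum test is not a remedy for unequal variances, and the rule invokes it as one. For roughly normal data the cost is small: about 5% to 7% rejections at equal means with equal arms, and about 7% to 7.5% in the less favourable unequal-arm case, with about 2 points of power lost against Welch in equal arms.

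The larger rates, about 9% to 17% at skewness 1 (SD ratio 1.5 to 2) and 26% to 33% at skewness 2 (SD ratio 1.5), need skew and unequal spread together and a reading in terms of means. Welch is near 5% to 6% in those settings. These are not forecasts of this trial's false-positive rate, since the documents give no SDs or distributions.

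The defect in the text itself is that the target is unstated, can change with a data-driven check, and comes with an undefined CI. The primary outcome is not affected.

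**What to change.** In SAP 6.1.2, delete the equal-variances condition and name Welch's t-test, with its mean difference and 95% CI, as the planned t-test for interval outcomes and multi-item totals. Assign the method to each outcome in Table 1 before unblinding and use it at all visits, with no assumption pre-tests. Where an outcome is assigned in advance to the rank-sum test (a single ordinal item, or one expected to be markedly skewed), report a matching measure and CI, such as the Hodges-Lehmann shift or the probability of superiority, and do not interpret it as a mean difference.

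This changes wording only. For roughly symmetric data there is no downside of note. For outcomes that are skewed with equal spread, Welch can have less power than the rank-sum test, so the choice between a mean and a rank target has to be made on purpose, outcome by outcome.
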